3.5 Safety Variables

3.5.1 Fetal Left Heart Growth

Change of dimensions of left heart structures and hemodynamics from the baseline fetal echo to the neonatal echo performed before the first postnatal intervention. The following variables will be analysed.

- Mitral valve diameter in diastole (z-score)
- Left ventricular inlet length (z-score)
- Direction of flow in the aortic arch (antegrade/retrograde)
- Left ventricular diastolic dimension (z-score)
- Left ventricular function
- Shunt direction through foramen ovale (left-to-right, right-to-left, bidirectional)

3.5.2 Fetal aortic valvuloplasty - technical details

The following details about the fetal cardiac intervention are among those that will be recorded:

• Type of maternal anesthesia

STATISTISKA KONSULTGRUPPEN	Statisti	cal Analysis Plan
Protocol: Effect of fetal aortic valvuloplasty on outcomes	Protocol No):
	Version: 1.0	Page 19 of 26

- Pre- and procedural fetal medication
- Fetal resuscitation drugs used
- Size of needle
- Number of cardiac punctures
- Diameter of balloon
- Balloon to aortic valve diameter ratio
- Inflation pressure
- Number of inflations
- Technical success by criteria

3.5.3 Fetal and maternal complications of fetal intervention

Safety of the prenatal procedure will be evaluated through the following variables:

- Intervention-related fetal death (defined as fetal death within 24 hours of procedure)
- Fetal death not directly related to the intervention, except termination of pregnancy
- Maternal complications to procedure (requiring intensive care or resulting in maternal death)
- Preterm delivery < 37 weeks
- Reasons for fetal or postnatal death

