2.1.6 Safety Population

All enrolled fetuses will be included in the safety population, also those wrongly included if such cases will exist.

Figure 5. Full analysis sets (FAS)

ToP=Termination of Pregnancy; IUD=Intrauterine Death; GW=Gestational Weeks; FAS=Full Analysis Set; FAV=Fetal Aortic Valvuloplasty

STATISTISKA KONSULTGRUPPEN	Statisti	cal Analysis Plan
Protocol: Effect of fetal aortic valvuloplasty on outcomes	Protocol No):
	Version: 1.0	Page 14 of 26

Figure 6. Per protocol populations (PP)

ToP=Termination of Pregnancy; IUD=Intrauterine Death; GW=Gestational Weeks; PP=Per Protocol; FAV=Fetal Aortic Valvuloplasty

Figure 7. Safety population

GW=Gestational Weeks; FAV=Fetal Aortic Valvuloplasty

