3.4.2 Secondary Efficacy Variables

Secondary efficacy variables in this study are as following:

- Transplantation-free survival from fetal diagnosis to 2 years of age (analysed as time to event on FAS_{ENR} (main analysis), FAS_{BIRTH} (followed from birth), PP_{ENR} and PP_{BIRTH} (followed from birth), overall for FAV 1+2 vs no-FAV 1+2 (main analysis), and descriptively FAV 1 vs no-FAV 1 and FAV 1 vs no-FAV 1+2).
- Survival from fetal diagnosis to live birth (analysed as time to event on FAS_{ENR} (main analysis) and PP_{ENR}, overall for FAV 1+2 vs no-FAV 1+2 (main analysis), and descriptively FAV 1 vs no-FAV 1 and FAV 1 vs no-FAV 1+2).

Protocol

Statistical Analysis Plan

Effect of fetal aortic valvuloplasty on outcomes

- Proportion of included patients who have a biventricular circulation at neonatal hospital discharge (analysed on FAS_{ENR} (main analysis), FAS_{BIRTH}, PP_{ENR} and PP_{BIRTH}, overall for FAV 1+2 vs no-FAV 1+2 (main analysis), and descriptively FAV 1 vs no-FAV 1 and FAV 1 vs no-FAV 1+2).
- Proportion of included patients who have a biventricular circulation at 2 years of age (analysed on FAS_{ENR} (main analysis), FAS_{BIRTH}, PP_{ENR} and PP_{BIRTH}, overall for FAV 1+2 vs no-FAV 1+2 (main analysis), and descriptively FAV 1 vs no-FAV 1 and FAV 1 vs no-FAV 1+2).
- Number of postnatal catheter and/or surgical procedures before 2 years of age (analysed on FAS_{BIRTH} (main analysis) and PP_{BIRTH}, overall for FAV 1+2 vs no-FAV 1+2 (main analysis), and descriptively FAV 1 vs no-FAV 1 and FAV 1 vs no-FAV 1+2).

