4 STATISTICAL METHODOLOGY

4.1 General Methodology

Continuous variables will be described by means, standard deviation (SD), median and range, and categorical by number and percentages.

Main analyses will be performed comparing FAV 1+2 versus no-FAV 1+2 groups on FAS_{ENR} population. Complementary analyses will be performed on FAS_{BIRTH}, PP_{ENR} and PP_{BIRTH}. Separate descriptive comparisons between FAV 1 vs no-FAV 1 and FAV 1 vs no-FAV 1+2 groups will also be performed.

Comparisons between the two groups with respect to demographics and baseline characteristics and safety data will be performed using Fisher's exact test for dichotomous variables, Mantel-Haenszel Chi-square test for ordered categorical variables, Chi-square test for non-ordered categorical variables, and Fisher's non-parametric permutation test for continuous variables.

Due to the non-randomised design, all analyses will be adjusted for confounders. It is important that all known confounders at the time of inclusion are defined. The main confounders will be gestational age at first diagnosis and at inclusion, morphology and hemodynamics of the fetal heart at the time of study inclusion and possibly some data about the mother's health which could have an impact on the chance of success with fetal intervention, such as BMI. Although the study is designed to minimize bias by using strict echocardiographic inclusion criteria, it will be necessary to analyse the groups at baseline carefully with respect to a number of selected echocardiographic variables describing the size and function of the left heart. If this analysis shows that, in spite of the strict inclusion criteria, there are significant differences between the groups regarding data that are at the same time risk factors for the studied outcomes the analyses will be adjusted for those additionally defined confounders besides the known ones. A sensitivity analysis will also be performed for the primary variable applying propensity score matching procedure (1:1 or 2:1 if possible) including all variables that are of importance (p<0.10 using logistic regression) for discrimination of FAV vs no-FAV group and those identified/known confounders in the adjusted analyses.

Known confounders are:

• Gestational age at primary diagnosis (earlier gestational age could indicate more severe disease, and might differ between countries and centres due to different

Protocol

Statistical Analysis Plan

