4.7.2 Intervention and Technical Details

Information about intervention and its technical details will be summarized on safety population per treatment groups.

Complications of fetal intervention and maternal complications 4.7.3

Data regarding complications and reasons for death will be described for safety population per treatment groups. No formal tests will be performed.

STATISTISKA KONSULTGRUPPEN	Statisti	cal Analysis Plan
Protocol: Effect of fetal aortic valvuloplasty on outcomes	Protocol No):
	Version: 1.0	Page 25 of 26

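### The only fetal-death safety row that both arms can fill leaves out FAV deaths in the first 24 hours, and no all-cause fetal-death row is listed for the safety population

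*SAP*

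**What the plan says.** Fetal and maternal safety is the only secondary objective (Protocol, Secondary objective; SAP 1.1). Both documents carry fetal mortality as the same two variables, repeated in SAP 3.5.3:

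- "Intervention-related fetal death (defined as fetal death within 24 hours of procedure"; and
- "Fetal death not directly related to the intervention, except termination of pregnancy".

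Only the first is defined. SAP 3.5.3 also lists "Reasons for fetal or postnatal death" as a separate variable. SAP 2.1.6 sets the denominator: "All enrolled fetuses will be included in the safety population", including any who were wrongly included. SAP 4.7.3 gives the analysis: "Data regarding complications and reasons for death will be described for safety population per treatment groups. No formal tests will be performed". SAP 4.1 says something different: group comparisons of "baseline characteristics and safety data will be performed using" Fisher's exact test and related tests.

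Outside the safety section, SAP 3.4.2 has a secondary efficacy variable without the 24-hour split: "Survival from fetal diagnosis to live birth (analysed as time to event on" FAS_ENR (main analysis) and PP_ENR. Under SAP 3.4.1 any death is a failure in the primary endpoint.

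**The concern.** The two rows will be read side by side by arm. The 24-hour row has no comparator, because a no-FAV fetus has no valvuloplasty from which to count. A reader looking for a two-arm comparison of fetal death therefore turns to the second row, where the arms are counted differently: no-FAV contributes every non-termination fetal death, and FAV contributes what is left after the first 24 hours. If the background risk is the same in both arms, that row must lean towards FAV.

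The label adds to this. The only stated criterion for relatedness is the clock. If the second row is the complement of the first, a death caused by the procedure but occurring after 24 hours is printed under a heading that denies a direct link. If the second row is instead judged by cause, such a death fits neither row. Either way the category needs a definition.

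At stake is whether the report on the safety objective shows, in one place and for everyone enrolled, how many fetuses died in each arm.

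**Working it through.** **1. Who can enter each row.** Procedure is taken to mean valvuloplasty, as the objective implies. The Protocol's exclusion criteria also admit fetuses with an atrial septal intervention and no valvuloplasty, so the SAP should say this explicitly.

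| Row | FAV 1+2 | no-FAV 1+2 |
|---|---|---|
| Within 24 h of procedure | deaths up to 24 h | none possible |
| Not directly related (complement reading) | deaths after 24 h | all fetal deaths |
| Sum (not listed in the SAP) | all fetal deaths | all fetal deaths |

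Terminations are outside all three rows.

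**2. Direction and size.** The plan states no fetal death rate, so there is no figure of its own to reproduce on this point. Let e be the proportion of FAV fetuses dying within 24 hours, and q the other fetal-death risk, assumed equal in both arms.

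- Second row, FAV minus no-FAV: (1 − e)q − q = −eq.
- All-cause, FAV minus no-FAV: e + (1 − e)q − q = e(1 − q).
- Gap between the two: e(1 − q) + eq = e.

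The second row thus understates the difference by exactly e, whatever q is. With assumed values:

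| e | q | Second row, FAV vs no-FAV | All-cause, FAV vs no-FAV |
|---|---|---|---|
| 2% | 4% | 3.92% vs 4% (−0.08 points) | 5.92% vs 4% (+1.92) |
| 5% | 8% | 7.6% vs 8% (−0.4) | 12.6% vs 8% (+4.6) |
| 10% | 12% | 10.8% vs 12% (−1.2) | 20.8% vs 12% (+8.8) |

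Over e = 2% to 10% and q = 4% to 12%, the second-row difference runs from −0.08 to −1.2 points. The all-cause difference runs from +1.76 points (e = 2%, q = 12%) to +9.6 points (e = 10%, q = 4%). The sign reverses throughout.

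**3. As counts at the planned 100 FAV and 50 no-FAV (SAP 1.5).** Assume 8 early and 6 later FAV deaths, and 3 no-FAV deaths.

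- Second row: 6/100 = 6% vs 3/50 = 6%.
- All-cause: 14/100 = 14% vs 6%, a risk difference of 8 points.
- Standard error: √(0.14 × 0.86/100 + 0.06 × 0.94/50) = 0.0483. The Wald 95% CI is 8 ± 9.5 points, or −1.5 to 17.5. Fisher p = 0.18.

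With 4 to 10 early and 4 to 6 later FAV deaths, the total is 4 + 4 = 8% to 10 + 6 = 16%, while the second row shows 4% to 6%.

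**4. What a test could add.** With q = 8% and 100 vs 50, Fisher's exact test has about 9% power for the all-cause difference at e = 5%, and about 30% at e = 10%. An estimate with an interval is more useful than a p-value.

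**5. Who the all-cause analyses cover.** Survival to live birth is on FAS_ENR and PP_ENR. SAP 2.1.1 takes out of FAS_ENR the high-risk fetuses (severe mitral regurgitation with severe left atrial enlargement, intact or highly restrictive atrial communication, or hydrops at inclusion) and those wrongly included. SAP 2.1.3 takes out of PP_ENR those with major protocol violations. Neither set is the safety population.

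**The case against.** The strongest reply is that nothing is lost. Early deaths have their own row, listed first, on the same population, and adding the two rows gives all non-termination fetal deaths. That stands. A reader might infer that the plan conceals procedural deaths, or that the safety comparison as a whole favours FAV. The documents support neither; only the second row, read alone, leans that way. Other safety variables, such as preterm delivery and left heart growth, have comparators in both arms.

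It can also be said that all-cause fetal death is already analysed through survival to live birth and the primary endpoint, and that SAP 4.6.3 describes these outcomes for the high-risk fetuses too. This stands in part. SAP 4.6.3 places that subgroup within FAS_ENR and FAS_BIRTH, from which SAP 2.1.1 and 2.1.2 exclude it. The primary endpoint mixes fetal death with circulation and pulmonary hypertension. The confirmatory sequence in SAP 4.1 words the survival variable as live birth at term, which SAP 3.4.2 does not.

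Third, a reader might infer a rule that every death after 24 hours is unrelated. The SAP does not say so: the second category is undefined, and recorded reasons for death are to be described (SAP 4.7.3, Table 3.2.1). The complement reading is natural, but it is an inference. The 24-hour rule is also objective and prespecified, and replacing it with attribution by recorded reason would be a debatable trade. The fix does not ask for that.

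Finally, a crude comparison on the safety population could be confounded against FAV, since SAP 2.1.1 expects high-risk fetuses to be overrepresented there. That stands and shapes the fix.

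**Conclusion.** The point holds as a matter of definition and presentation. The one fetal-death row that both arms can fill is not like-for-like, its label describes cause where the only stated criterion is time, and no all-cause fetal-death row is listed for the population meant to hold everyone enrolled. The row understates the FAV minus no-FAV difference by the early-death proportion e.

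That identity rests on the complement reading; the lean towards FAV also assumes equal background risk. It ignores that FAV membership starts at needle introduction (SAP 1.4). All the rates and counts are assumptions. They do not show that fetal mortality is higher with FAV: even the 14% vs 6% example has an interval that includes zero. This is a worthwhile, inexpensive improvement to the report on the only secondary objective, not a flaw that invalidates the safety analysis.

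**What to change.** In SAP 3.5.3, SAP 4.7.3 and Table 3.2.1:

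- Add all-cause fetal death, with terminations shown separately, for FAV 1+2 vs no-FAV 1+2 on the safety population. Give a descriptive risk difference with 95% CI, overall and separately for high-risk and non-high-risk fetuses.
- Keep death within 24 hours of the procedure as a FAV-only row, and state which procedure starts the clock.
- Define the second row and name it by timing: more than 24 hours after the procedure in FAV, any fetal death in no-FAV.
- For FAV deaths, list the time from procedure to death beside the recorded reason.
- Reconcile SAP 4.1, which applies tests to safety data, with SAP 4.7.3, which rules them out for complications.

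The cost is SAP wording, an extra table row with its stratified display, and a short listing. Intervention forms and reasons for death are already part of the planned data. The drawback for the sponsor is that FAV's displayed fetal mortality may look less favourable than in the second row alone. No clinical management changes.

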3.5.4 Events

All postnatal cardiac surgical or catheter interventions from birth to 2 years of age will be listed.

Protocol

Statistical Analysis Plan

4 STATISTICAL METHODOLOGY

4.1 General Methodology

Continuous variables will be described by means, standard deviation (SD), median and range, and categorical by number and percentages.

Main analyses will be performed comparing FAV 1+2 versus no-FAV 1+2 groups on FAS_{ENR} population. Complementary analyses will be performed on FAS_{BIRTH}, PP_{ENR} and PP_{BIRTH}. Separate descriptive comparisons between FAV 1 vs no-FAV 1 and FAV 1 vs no-FAV 1+2 groups will also be performed.

Comparisons between the two groups with respect to demographics and baseline characteristics and safety data will be performed using Fisher's exact test for dichotomous variables, Mantel-Haenszel Chi-square test for ordered categorical variables, Chi-square test for non-ordered categorical variables, and Fisher's non-parametric permutation test for continuous variables.

Due to the non-randomised design, all analyses will be adjusted for confounders. It is important that all known confounders at the time of inclusion are defined. The main confounders will be gestational age at first diagnosis and at inclusion, morphology and hemodynamics of the fetal heart at the time of study inclusion and possibly some data about the mother's health which could have an impact on the chance of success with fetal intervention, such as BMI. Although the study is designed to minimize bias by using strict echocardiographic inclusion criteria, it will be necessary to analyse the groups at baseline carefully with respect to a number of selected echocardiographic variables describing the size and function of the left heart. If this analysis shows that, in spite of the strict inclusion criteria, there are significant differences between the groups regarding data that are at the same time risk factors for the studied outcomes the analyses will be adjusted for those additionally defined confounders besides the known ones. A sensitivity analysis will also be performed for the primary variable applying propensity score matching procedure (1:1 or 2:1 if possible) including all variables that are of importance (p<0.10 using logistic regression) for discrimination of FAV vs no-FAV group and those identified/known confounders in the adjusted analyses.

Known confounders are:

• Gestational age at primary diagnosis (earlier gestational age could indicate more severe disease, and might differ between countries and centres due to different

Protocol

Statistical Analysis Plan

Effect of fetal aortic valvuloplasty on outcomes

Protocol No:

screening policies) and gestational age at inclusion. Most probably they are highly correlated and in that case the more influential of the two will be used.

Variables listed under 3.1 as potential confounders will be investigated whether they are important for discriminating FAV vs no-FAV and whether they are confounders (associated p<0.10 both to the group and the outcome).

Dichotomous outcome variables will be analysed using logistic regression, adjusted for identified confounders available at the time of study inclusion. Odds-ratios (OR) with 95% confidence intervals (CI) will be presented.

Time-to-event analyses will be performed using Cox proportional hazards models adjusting for identified confounders. Proportional hazards assumption will be checked by visually reviewing log(-log(survival)) vs log(time) graphs, and by adding interaction between treatment group and log(time) in the model, where significant interaction indicates non-proportionality. Other methods will be applied, e.g. Poisson regression for time varying data, allowing study of changes in treatment effects over follow-up time, in case non-proportionality of hazards occurs.

Time-to-event data will be described by using Kaplan-Meier technique.

The primary analyses for the FAV vs no-FAV group conducted on FAS_{ENR} population will be considered as confirmatory analyses and a total significance mass of 0.05 will be applied. The tests will be performed on the primary variable and the most important secondary variables using fix sequential testing procedure according to the following order:

1. Primary variable: Transplantation-free survival from fetal diagnosis to 2 years postnatal age, having a biventricular circulation without pulmonary hypertension at that time

2. Secondary variable: Transplantation-free survival from fetal diagnosis to 2 years of age

3. Secondary variable: Survival from fetal diagnosis to live birth at term (≥37 weeks)

4. Secondary variable: Proportion of included fetuses who have a biventricular circulation at neonatal hospital discharge

5. Secondary variable: Proportion of included fetuses who have a biventricular circulation at 2 years of postnatal age

This means that first test must be significant on 0.05 significance level in order to be able to further confirm the tests 2 to 5, and the second test must be significant on 0.05 level in order to be able to confirm tests number 3 to 5, etc.

Protocol

Statistical Analysis Plan

Effect of fetal aortic valvuloplasty on outcomes

Analysis of longitudinal change of left heart size and function, will be conducted in an exploratory manner. This will be investigated using mixed models for repeated data, with normal distribution for z-scores and binomial distribution for binary variables, handling time in study both as distinct visits and continuous (gestational age) as found most appropriate. Linear and non-linear models will be investigated. Model selection will be based on lowest goodness of fit statistics, e.g. Akaike's Information Criterion. Even though a p<0.05 the tests will not be considered confirmed, since not included in the multiplicity corrections above. Estimates, 95% CI, and p-values will be evaluated for descriptive purpose.

All tests will be two-tailed. All analyses will be performed by using SAS software version 9.4 or later (SAS Institute Inc., Cary, NC, USA).

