1.4 Study Groups

The main analysis comparing intervention versus non-intervention will be on an intention-totreat, i.e. intention to perform fetal aortic valvuloplasty, basis. Intention to perform fetal valvuloplasty is defined as being present if the needle has been introduced through the maternal abdominal wall even if the fetal thorax has not been touched. Subjects will be Protocol

Statistical Analysis Plan

1.0

identified as belonging to the fetal aortic valvuloplasty (FAV) or the no-FAV groups as listed below.

The following groups will be identified:

- Subjects that undergo a technically successful fetal aortic valvuloplasty at a high volume intervention centre (FAV 1).
- Subjects with intention-to-treat (according to the above definition) at a high volume intervention centre but with no technical success (FAV 2).
- Subjects counselled at a center not performing or referring for fetal aortic valvuloplasty (no-FAV 1).
- Subjects counselled at a high- or low-volume intervention center, or at a center offering referrals to a center performing interventions, and the parental decision is to not perform fetal aortic valvuloplasty (no-FAV 2).

The main analyses will be to compare FAV 1+2 versus no-FAV 1+2. The expected proportion of enrolled fetuses/infants will be 2 [FAV] : 1 [no-FAV]. Complementary analyses will be comparing FAV 1 versus no-FAV 1, and FAV 1 versus no-FAV 1+2.

Figure 4. Main and complementary analysis

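### SAP 4.1 tests safety data with Fisher's exact test while 4.7.3 rules out tests of complications; for events defined by the procedure the p-value would depend on the number of controls, and no confidence interval is planned for these risks.

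*SAP*

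**What the plan says.** SAP 4.1 (General Methodology) sets one testing rule for several kinds of data: "Comparisons between the two groups with respect to demographics and baseline characteristics and safety data will be performed using Fisher's exact test" for dichotomous variables, with other tests for ordered, non-ordered and continuous variables. It makes no exception for any safety variable. The same section says that all analyses will be adjusted for confounders.

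SAP 4.7.3 deals with complications directly: "Data regarding complications and reasons for death will be described for safety population per treatment groups". It then adds: "No formal tests will be performed".

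SAP 3.5.3 lists the variables concerned. Two are defined by the procedure: "Intervention-related fetal death (defined as fetal death within 24 hours of procedure" and "Maternal complications to procedure (requiring intensive care or resulting in maternal death". Two can occur in either group: "Fetal death not directly related to the intervention, except termination of pregnancy", and delivery before 37 weeks. SAP 1.4 fixes who is in the FAV group: "Intention to perform fetal valvuloplasty is defined as being present if the needle has been introduced through the maternal abdominal wall".

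For description, SAP 4.1 provides numbers and percentages for categorical variables. Its 95% confidence intervals are for adjusted odds ratios of dichotomous outcomes. No interval for a complication rate appears in 4.1, 4.7.3 or the table list (Tables 3.2.1 and 3.2.2).

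**The concern.** Fetal and maternal safety is the secondary objective, and the protocol (Publication of results) makes it a subject of a possible first paper. For complications and deaths the SAP gives two instructions and no order of precedence. An analyst could follow either and claim to have followed the plan, so the choice could be made after the data are seen.

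Each route has a weakness. Under 4.1, the two procedure-defined events would be tested against a group in which they cannot happen. The result would depend on how many controls were recruited, which says nothing about the risk of the procedure. Under 4.7.3, the reader gets a count and a percentage without a statement of how high the risk could be. With about 100 procedures, a low or zero count is compatible with a risk that matters to parents.

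**Working it through.** **Inputs.** 100 FAV with 50 or 100 no-FAV, and two-sided alpha 0.05 (SAP 1.5); two-tailed tests (SAP 4.1); event definitions (SAP 3.5.3). The documents give no expected rate for any safety event.

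**1. The plan's own Fisher figures.** SAP 1.5 gives power for the primary endpoint only, at 60% vs 30%. Exact enumeration of two binomials gives:

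| FAV : no-FAV | SAP | Recomputed |
|---|---|---|
| 100 : 50 | 91.8% | 92.7% (92.0% with the doubled one-sided p) |
| 100 : 100 | 98.7% | 98.9% |

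Agreement is within one percentage point, so the same test is used below.

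**2. Why zero is fixed.** A no-FAV case has no attempted valvuloplasty from which to count 24 hours, or to which a maternal complication could be attributed. The control count is 0 whatever the data show.

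**3. Fisher p for k events in 100 FAV against 0 in m controls.** With the total k fixed, the number X falling in FAV is hypergeometric:

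P(X=j) = C(100,j) × C(m,k−j) / C(100+m,k).

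The two-sided p sums all terms no larger than P(X=k).

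- m=50, k=8: P(X=8)=0.0354. The terms for j=0, 1, 2 are 0.0001, 0.0019 and 0.0150. The sum is 0.0524.
- m=100, k=8: P(X=8)=0.0034 and P(X=0)=0.0034. The sum is 0.0068, or 0.007.

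| k in 100 FAV | vs 0/50 | vs 0/100 |
|---|---|---|
| 5 | 0.170 | 0.059 |
| 6 | 0.179 | 0.029 |
| 7 | 0.096 | 0.014 |
| 8 | 0.052 | 0.007 |
| 9 | 0.030 | 0.003 |

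The largest non-significant count is 8 with 50 controls, 6 with 60, and 5 with 70 to 100. The doubled one-sided version gives the same cut-off at 100:50 (k=8: 0.071; k=9: 0.046). At k=8 the observed risk is 8% in every column; only the number of controls differs.

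**4. Chance of p>0.05 if the test were applied.** This is P(X≤8) with 50 controls and P(X≤5) with 100, where X is binomial with n=100. The true rates are assumptions chosen to show a range.

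| Assumed true rate | 50 controls | 100 controls |
|---|---|---|
| 5% | 94% | 62% |
| 8% | 59% | 18% |
| 10% | 32% | 6% |

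**5. One-group description.** Exact (Clopper-Pearson) 95% limits do not involve the controls.

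- 0/100: upper limit = 1 − 0.025^(1/100) = 3.6%.
- 8/100: 3.5% to 15.2%.

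**The case against.** The strongest reply is that a specific section overrides a general one. Section 4.7.3 is the only text on how complications and deaths are analysed, and it rules out tests. On that reading none of the p-values above would be produced. This is a sensible reading, but the SAP does not state it.

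It can also be said that the two sentences need not collide. In this SAP, safety data include the left-heart variables of 3.5.1, which span several of the variable types in the 4.1 sentence. The sentence could apply there while 4.7.3 exempts complications. That stands, and it is why the remedy is to limit the phrase, not to delete it.

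Fetal death and prematurity are also covered elsewhere. Survival to live birth is a secondary variable (3.4.2), and live birth at term is third in the confirmatory sequence (4.1), analysed by adjusted Cox regression. Fetal death also counts against the primary endpoint. So a Fisher test would not be the only comparison for these events. These analyses use FAS_ENR as the main population, which leaves out the high-risk cases, and they do not isolate procedural risk.

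The odds-ratio intervals in 4.1 do not fill the gap. With a group fixed at zero, ordinary logistic regression has no finite odds ratio, and an odds ratio is not the risk of the procedure.

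A reader might infer that the SAP plans to declare up to 8 procedure-related deaths in 100 not significant, and hence acceptable. The documents do not support this. It requires 4.1 to prevail over 4.7.3 and exactly the minimum of 50 controls, and no passage concludes safety from a p-value above 0.05.

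**Conclusion.** The point holds as an unresolved contradiction, with a gap in reporting that remains whichever section is followed. It is not a settled plan to test procedural deaths.

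If 4.1 were applied, the p-value for procedure-defined events would be uninterpretable: the same 8% risk gives p=0.052 or p=0.007 depending on whether 50 or 100 controls are enrolled. If 4.7.3 governs, the remaining defect is that no interval is planned for two procedural risks within the secondary objective.

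The figures assume 100 FAV cases and 50 to 100 controls. The safety population is all enrolled fetuses (SAP 2.1.6), so its final size may differ. The rates in step 4 are assumed. The fixed zero assumes that procedure in 3.5.3 means the valvuloplasty, in line with the secondary objective; the protocol (Exclusion criteria) also admits cases with an atrial septal intervention and no valvuloplasty. The fixed-zero argument does not extend to other fetal deaths or preterm delivery, where comparison is meaningful.

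**What to change.** - **SAP 4.1:** exclude the complications and deaths of 3.5.3 from the testing sentence, so that it agrees with 4.7.3. The sentence can still apply to other safety data.
- **SAP 4.7.3 and Tables 3.2.1 and 3.2.2, procedure-defined events:** report intervention-related fetal death and maternal complications among attempted valvuloplasties (FAV 1+2) only, as counts and proportions with exact 95% confidence intervals. State that procedure means attempted valvuloplasty.
- **Same places, events possible in both groups:** for other fetal deaths and preterm delivery, give between-group estimates with 95% confidence intervals. Adjust for the confounders already identified where event counts allow, and show results with and without the high-risk population. SAP 2.1.1 expects high-risk cases to be overrepresented in FAV, so a crude difference in the safety population would mix disease severity with procedural harm. Label any crude difference as descriptive.

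The cost is SAP wording and added table columns, with no new data. The intervals will be wide and should be reported as such. Adjustment may not be possible if events are few.
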